11.2.2 Serious Adverse Events (SAEs)

11.2.2.1 Site Requirements for Reporting SAEs to Big Ten CRC Administrative Headquarters

• SAEs will be reported from time of signed informed consent until 30 days after discontinuation of study drug(s) or until a new anti-cancer treatment starts, whichever occurs first.

- SAEs will be reported on the SAE Submission Form and entered in the SAE tab in the EDC system within 1 business day of discovery of the event.
- SAEs include events related and unrelated to the study drug(s).
- All SAEs will be recorded in the subject's medical record and on the appropriate study specific eCRF form within the EDC system.
- All SAEs regardless of relation to study drug will be followed until resolution to ≤ Grade 1 or baseline and/or deemed clinically insignificant and/or until a new anti-cancer treatment starts, whichever occurs first.

The site will submit the completed SAE Submission Form (see Documents/Info tab in the EDC) to Big Ten CRC AHQ within **1 business day** of discovery of the event. The form will be sent electronically to Big Ten CRC AHQ at [contact]. The site investigator is responsible for informing the IRB and/or other local regulatory bodies of the SAE as per local requirements.

The original copy of the SAE Submission Form and the email correspondence must be kept within the study file at the study site.

Once the SAE has resolved, sites must electronically submit a follow up SAE Submission Form within a reasonable timeframe to Big Ten CRC AHQ at [contact].

11.2.2.2 Big Ten CRC AHQ Requirements for Reporting SAEs to Ipsen Biopharmaceuticals

Big Ten CRC AHQ will report SAEs to Ipsen Biopharmaceuticals within **1 business day** of receipt of the SAE Submission Form from a site. Follow-up information will be provided to Ipsen Biopharmaceuticals within one business day of receipt from a site. The information will be reported through one of the following communication methods:

Ipsen Pharmacovigilance contact: Ipsen Call Center Telephone (24 Hours/7 Days): [contact] [contact] Emergency: [contact] Affiliate general PV mailbox: [contact]

11.2.2.3 Sponsor-Investigator Responsibilities

Big Ten CRC AHQ will send a SAE summary to the sponsor-investigator **within 1 business day** of receipt of SAE Submission Form from a site. The sponsor-investigator will promptly review the SAE summary and assess for expectedness and relatedness.

11.2.2.4 Big Ten CRC AHQ Responsibilities for Reporting SAEs to FDA

The FDA has concluded this protocol is exempt from the requirements of an IND. Big Ten CRC AHQ will continue to facilitate compliance of applicable requirements for the sponsor-investigator in relation to this study. This includes but is not limited to 21 CFR 50.20 informed consent, 21 CFR Part 56 IRB, and pertinent sections of the Public Health Service Act and FDAAA.

11.2.2.5 IND Safety Reports Unrelated to this Trial

Ipsen Biopharmaceuticals will provide Big Ten CRC AHQ with IND safety reports from external studies that involve the study drug(s) per their guidelines. Big Ten CRC AHQ will forward the safety reports to the sponsor-investigator who will review these reports and determine if revisions are needed to the protocol or consent. Big Ten CRC AHQ will forward these reports to participating sites **within 1 business day** of receiving the sponsor-investigator's review. Based on the sponsor-investigator's review, applicable changes will be made to the protocol and informed consent document (if required). All IND safety reports will also be made available to sites via the EDC system.

Upon receipt from Big Ten CRC AHQ, site investigators (or designees) are responsible for submitting these safety reports to their respective IRBs, as per their IRB policies.

12. STATISTICAL METHODS

12.1 Study Design

This is a phase II, single-arm, open-label, clinical study to investigate the efficacy and tolerability of a combination of liposomal irinotecan (nal-IRI) with oxaliplatin, leucovorin, and 5-fluorouracil (FOLFOX-nal-IRI) for treatment of patients with locally advanced pancreatic carcinoma (LAPC).

12.2 Endpoints

12.2.1 Definition of Primary Endpoint

Disease control rate (DCR) as determined by the proportion of subjects with complete response, partial response, or stable disease, at 24 weeks following initiation of FOLFOX-nal-IRI.

12.2.2 Definition of Secondary Endpoints

- Objective response rate (ORR) as determined by the proportion of subjects with either complete response or partial response as defined by RECIST 1.1 at 8 weeks, 16 weeks, and 24 weeks following initiation of FOLFOX-nal-IRI.
- Stable disease rate (SDR) as determined by the proportion of subjects with no progression of disease as defined by RECIST 1.1, at 8 weeks, 16 weeks, and 24 weeks following initiation of FOLFOX-nal-IRI.
- Rate of resectability as determined by the proportion of subjects who undergo surgical resection of tumors.
- The serum levels of CA 19-9 prior to initiation of chemotherapy and after every 2 cycles (every 4 weeks) following initiation of FOLFOX-nal-IRI.
- Progression-free survival (PFS) as determined by the time interval from the date of first dose of study drug to first documented disease progression or death from any cause, whichever occurs first, if evaluable.
- Overall survival (OS) as defined as the time interval from the date of the first dose of study drug to date of death from any cause.
- Safety and tolerability of FOLFOX-nal-IRI; Grade 3 and 4 toxicities as defined by the NCI Common Terminology Criteria for Adverse Events (NCI CTCAE) v5.

• Quality of life as measured at baseline and after every 4 cycles (every 8 weeks) using the European Organization for Research and Treatment of Cancer Quality-of-Life Core Questionnaire (EORTC-QLQ-C30).

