2.2 Endpoints

2.2.1 Primary Endpoint

Disease control rate (DCR) as determined by the proportion of subjects with complete response, partial response, or stable disease, as defined by RECIST 1.1, at 24 weeks following initiation of FOLFOX-nal-IRI (for the subjects whose tumors remain unresectable following 12 cycles of FOLFOX-nal-IRI).

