1: Medical History (clinically significant medical history as determined by the treating physician); other data to be obtained includes: diagnosis and staging (pathology report and staging documentation [TNM staging]), smoking history questionnaire and trial awareness question, prior anticancer treatment including medications, [chemotherapy, checkpoint inhibitors, etc.], radiation and surgery.

2: Vital signs to include blood pressure, weight, and height (screening only) and ECOG performance status

3: Assessment of quality of life: prior to treatment on Cycle 1 Day 1 then after every 4 cycles of FOLFOX-nal-IRI (every 8 weeks) and at the safety follow up visit. If a cycle is delayed, QOL assessment should also be delayed. Assessment will be done using the EORTC-QLQ-C30.

4: CMP to include sodium, potassium, chloride, creatinine, blood urea nitrogen; liver function tests (LFTs) to include AST, ALT, total bilirubin, alkaline phosphatase. CBC with differential and platelet count to include WBC, Hgb, ANC and platelet count.

5: CA19-9 will be drawn prior to treatment on Cycle 1 Day 1 then after every 2 cycles of FOLFOX-nal-IRI (that is, every 4 weeks) and at the safety follow up visit. If a cycle is delayed, CA19-9 should also be delayed.

6: For women of childbearing potential (WOCBP): serum β hCG, within 7 days prior to study registration. WOCBP must also have a negative serum pregnancy test within 72 hours of Cycle 1 Day 1.

7: Tumor response will be performed at screening then after every 4 cycles (every 8 weeks); tumor imaging to be done at treatment discontinuation at discretion of investigator. CT pancreas triple phase with pelvis and chest CT may replace the CT chest-abdomen-pelvis if clinically indicated. Baseline bone scan will be obtained if there is any suspicion of metastatic bone involvement. If bone scan is positive at baseline, subjects will be excluded from the study. A screening MRI of brain should be performed to evaluate for the presence of brain metastases as clinically indicated. A CT scan of the brain may be done if MRI is contraindicated. A \pm 7-day window will apply to all imaging.

8: If prior genetic sequencing results were performed as per standard of care, they will be submitted at C1D1. See also Section 8.1. If the subject undergoes surgical resection, tissue will be required from that procedure. All specimens will be used for biospecimen-based research.

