9.5 Evaluation of Target Lesions

NOTE: In addition to the information below, also see section 4.3.2 in the international criteria proposed by the Response Evaluation Criteria in Solid Tumors (RECIST) Committee, version 1.1 (Eur J Cancer 45;2009:228-247) for special notes on the assessment of target lesions.

Complete	Disappearance of all target lesions. Any pathological lymph
Response (CR)	nodes (whether target or non-target) must have reduction in
	short axis to <10 mm.
Partial Response	At least a 30% decrease in the sum of the diameters of target
(PR)	lesions, taking as reference the baseline sum diameters
Progressive	At least a 20% increase in the sum of the diameters of target
Disease (PD)	lesions, taking as reference the smallest sum on study (this
	includes the baseline sum if that is the smallest on study). In
	addition to the relative increase of 20%, the sum must also
	demonstrate an absolute increase of at least 5 mm. (Note: the

	appearance of one or more new lesions is also considered progressions).
Stable Disease	Neither sufficient shrinkage to qualify for PR nor sufficient
(SD)	increase to qualify for PD, taking as reference the smallest sum
	diameters while on study

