9.7 Evaluation of Overall Response

Target Lesions	Non-Target Lesions	New Lesions	Overall Response	
CR	CR	No	CR	
CR	Non-CR/ Non-PD	No	PR	
CR	Not evaluated	No	PR	
PR	Non-PD/ or not all evaluated	No	PR	
SD	Non-PD or not all evaluated	No	SD	
Not all evaluated	Non-PD	No	Non-evaluable	
PD	Any	Yes or No	PD	
Any	PD*	Yes or No	PD	
Any	Any	Yes	PD	
*In exceptional circumstances, unequivocal progression in non-target lesions may be accepted as disease progression.				

Subjects with a global deterioration of health status requiring discontinuation of treatment without objective evidence of disease progression at that time should be classified as having "symptomatic deterioration". Every effort should be made to document the objective progression even after discontinuation of treatment.

In some circumstances, it may be difficult to distinguish residual disease from normal tissue. When the evaluation of complete response depends on this determination, it is recommended that the residual lesion be investigated (fine needle aspirate/biopsy) to confirm the complete response status.

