9.8.2 Confirmation of Response

To be assigned a status of complete or partial response, changes in tumor measurements must be confirmed by repeat assessments performed no less than four weeks after the criteria for response are first met.

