9.8.3 Objective Response Rate

The objective response rate is the proportion of all subjects with confirmed PR or CR according to RECIST 1.1, from the start of treatment until disease progression/recurrence (taking as reference for progressive disease the smallest measurements recorded since the start of treatment).

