9.8.4 Disease Control Rate

The disease control rate is the proportion of all subjects with stable disease (SD) for 8 weeks, or partial response (PR), or complete response (CR) according to RECIST 1.1, from the start of treatment until disease progression/recurrence (taking as reference for progressive disease the smallest measurements recorded since the start of treatment).

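### The stable disease rate is defined as absence of progression, so as written it counts CR and PR as stable disease and overlaps with the objective response rate

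*Combined protocol and SAP*

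**What the plan says.** The endpoint lists in sections 2.2.2 and 12.2.2 carry the same definition: "Stable disease rate (SDR) as determined by the proportion of subjects with no progression of disease as defined by RECIST 1.1", assessed at weeks 8, 16 and 24. The bullet directly above it in each list defines ORR as CR or PR at the same time points. Section 12.6.2, the analysis plan for the secondary objectives, adds no rule of its own and refers the analyst to 12.2.2.

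Everywhere else the document treats SD as a category apart from response:

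- Section 9.5 describes SD in the target lesions as "Neither sufficient shrinkage to qualify for PR nor sufficient" growth for progressive disease (PD).
- Section 9.7 gives SD its own row in the overall-response table, "SD Non-PD or not all evaluated No SD" (target lesions, non-target lesions, new lesions, overall response). CR, PR, non-evaluable and PD are separate outcomes.
- Section 2.2.1 builds the primary endpoint from "complete response, partial response, or stable disease, as defined by RECIST 1.1, at 24 weeks following initiation of FOLFOX-nal-IRI", and section 9.8.4 from "stable disease (SD) for 8 weeks, or partial response (PR), or complete response (CR"). Section 12.2.1 likewise names the three components one by one.
- Section 12.6.1 takes ORR and SDR from two cited studies and adds them to give each study's DCR.

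**The concern.** The definition and the name of the endpoint describe different sets of subjects. Not having progressed covers CR, PR and SD together; stable disease covers SD alone. An analyst who codes section 12.2.2 as it stands will count every subject not in PD. An analyst who works from the overall-response table in 9.7 will count only those rated SD. Each can claim to have followed the plan, and they will report different rates.

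At stake is the correctness of a named secondary result at three time points, which section 13.4 requires to be posted publicly. A reader of the posted results would expect ORR and SDR to be separate and to add up to disease control, as they do in 12.6.1. Under the literal definition they would not.

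**Working it through.** **Inputs, all from section 12.6.1**

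| Cited study | ORR | SDR | DCR |
|---|---|---|---|
| Gemcitabine alone | 5% | 35% | 40% |
| Modified FOLFIRINOX | 18.8% | 56.2% | 75% |

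**Step 1. Reproduce the plan's own figures.** The plan obtains DCR as ORR + SDR.

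- Gemcitabine: 5 + 35 = 40%.
- Modified FOLFIRINOX: 18.8 + 56.2 = 75.0%.

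Both agree with the stated values. The sum is valid only if no subject is in both terms, that is, if SDR means SD alone.

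**Step 2. Apply the wording of 2.2.2 and 12.2.2.** Among subjects with an evaluable response, let c, p and s be the proportions in CR, PR and SD.

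- ORR = c + p
- SDR meaning SD alone = s
- SDR as worded (not progressed) = c + p + s
- Excess of the worded SDR = c + p = ORR
- ORR + SDR as worded = 2(c + p) + s = DCR + ORR

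So the literal rule overstates SDR by exactly the ORR, whatever the ORR turns out to be.

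**Step 3. Put in the cited figures, as an illustration only.**

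| Cited study | SDR, SD alone | SDR as worded | Excess (points) | ORR + SDR as worded | DCR |
|---|---|---|---|---|---|
| Gemcitabine alone | 35% | 5 + 35 = 40% | 5 | 5 + 40 = 45% | 40% |
| Modified FOLFIRINOX | 56.2% | 18.8 + 56.2 = 75% | 18.8 | 18.8 + 75 = 93.8% | 75% |

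In both rows the worded SDR equals the DCR, so it carries no information beyond disease control.

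**Step 4. Look for text that narrows the definition.** Section 12.6.2 refers back to 12.2.2. Sections 9.8.3 and 9.8.4 define ORR and DCR; section 9.8 has no entry for SDR. No other section restates SDR as SD alone.

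**The case against.** The strongest reply is that nobody would be misled. The endpoint is called a stable disease rate, RECIST 1.1 is cited, ORR stands in the line above, and every other section points to SD alone. SDR carries no hypothesis, threshold or stopping rule; section 2.1.2 only asks that it be described. The overall responses in section 9.7 keep SD apart at each assessment, so the right rate can be derived at reporting with no loss of data.

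Much of this stands. The intent can be inferred, no data are lost, and the matter is one of wording. What does not stand is that the documents already settle it. In the definition, the reference to RECIST 1.1 qualifies progression, not stable disease. Section 12.6.2 makes that definition the operative rule. A stated rule that gives a wrong reported rate should be corrected, not left to inference.

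A reader might go further and infer three things that the documents do not support.

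- **That some responses will fall between ORR and SDR.** Section 9.8.3 says "The objective response rate is the proportion of all subjects with confirmed PR or CR according to RECIST 1.1", section 9.8.2 says "changes in tumor measurements must be confirmed by repeat assessments performed no less than four weeks after" the criteria are first met, and the calendar says "Tumor response will be performed at screening then after every 4 cycles (every 8 weeks"). A response first seen at week 24 could therefore be confirmed at week 28 at the earliest, after the last scheduled on-treatment scan. But the four weeks is a minimum with no maximum. Footnote 7 of the calendar allows imaging at treatment discontinuation at the investigator's discretion, and section 7.2 follows non-progressors every 3 months for 1 year. Such a case is possible, not established. It is also a question about confirming ORR, not a result of the SDR wording.
- **That the 8-week SD duration in 9.8.4 leaves SDR undefined.** The first response scan falls at about week 8, so SD at any of the three time points meets that duration almost by construction, apart from the 7-day imaging window.
- **That a definite number of subjects will be double-counted.** Applying the cited ORRs to 25 subjects gives 0.05 × 25 = 1.25 to 0.188 × 25 = 4.7. But 12.6.1 does not say whether those ORRs are best-response or time-point rates, and nothing establishes that 25 subjects will have a response category at week 24.

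**Conclusion.** The point holds as an error of definition in a descriptive secondary endpoint. As written, SDR is a non-progression rate that exceeds the SD-only rate by the ORR: 5 and 18.8 percentage points at the cited studies' figures. These sizes assume that the cited ORR and SDR are exclusive categories, as 12.6.1 treats them. They show the mechanism and do not forecast this trial's results.

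A reader might infer that the primary result is compromised. It is not. DCR counts CR, PR and SD together, so how responders are split from SD does not change it. The sample size and both decision rules (stop at 5 or fewer of 12; success at 16 or more of 25) do not use SDR.

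Nor does the worded SDR at week 24 duplicate the primary endpoint in every form. It essentially matches DCR as defined in 12.2.1 among evaluable subjects. It does not match 2.2.1, which is restricted to subjects still unresectable after 12 cycles, or 9.8.4, which uses SD for 8 weeks.

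**What to change.** In sections 2.2.2 and 12.2.2, replace the phrase about absence of progression so that SDR is the proportion of subjects with *an overall response of stable disease (not CR, PR, PD or non-evaluable)* as defined by RECIST 1.1 (section 9.7), at 8, 16 and 24 weeks. Naming the excluded categories separates SDR from ORR and also keeps an assessment without a usable response out of the numerator.

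The cost is one phrase in two places, best changed before results are tabulated. Data collection, sample size, the interim rule and the primary analysis stay as they are.

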1.3.3.1 Safety

The safety data for irinotecan liposome injection are described in detail in the investigator brochure. The most common adverse reactions (≥ 20 %) considered to be related to treatment observed in clinical trials of irinotecan liposome injection in combination with 5-fluorouracil and leucovorin, are: diarrhea, fatigue/asthenia, vomiting, nausea, decreased appetite, stomatitis, and pyrexia. The most common laboratory abnormalities ($\geq 10\%$ Grade 3 or 4) were lymphopenia and neutropenia (ONIVYDE[®] USPI). The most common serious adverse reactions ($\geq 2\%$) of irinotecan liposome injection were diarrhea, vomiting, febrile neutropenia, nausea, pyrexia, sepsis, dehydration, septic shock, pneumonia, acute renal failure and thrombocytopenia

(ONIVYDE[®] European SPC).

The safety of irinotecan liposome injection, a liposomal formulation of irinotecan, may be indirectly compared with the safety of irinotecan, primarily based on a qualitative comparison of adverse reactions reported in the Camptosar[®] US label for irinotecan and in the US Product Label for ONIVYDE[®]. The most common adverse reactions of irinotecan and irinotecan liposome injection are similar and are mainly gastrointestinal events and myelosuppression.

Certain known adverse reactions of irinotecan, including anaphylaxis or anaphylactoid reaction, interstitial lung disease-like pulmonary toxicity, and acute pancreatitis, have not been observed with irinotecan liposome injection to date. This could be due to the limited cumulative patient exposure to date of irinotecan liposome injection, or the use of appropriate premedication and early recognition and treatment of expected adverse events. There is insufficient evidence to know whether these known adverse reactions of irinotecan will eventually be associated with irinotecan liposome injection.

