1.3.3.1.1 Safety Data from Ongoing MM-398-07-02-03 Study

A Randomized, Open-label Phase 2 Study of Nanoliposomal Irinotecan (nal-IRI)-containing Regimens versus nab-paclitaxel plus Gemcitabine in Patients with Previously Untreated, Metastatic Pancreatic Adenocarcinoma (NCT02551991)

This study is an open-label, phase II study to assess the safety, dose-limiting toxicities (Part 1A only), tolerability, and preliminary efficacy of irinotecan liposome injection in combination with oxaliplatin+5-FU/LV in subjects with metastatic pancreatic adenocarcinoma who have not received prior systemic anti-tumor therapy. The study comprises an initial dose exploration (Part 1A) followed by dose expansion (Part 1B ongoing in the extension phase) of the irinotecan liposome injection+ oxaliplatin+5-FU/LV regimen.

For the 56 subjects treated, all (100.0%) had treatment-emergent adverse events (TEAEs). There were nine TEAEs that were defined as Dose Limiting Toxicities (DLTs) that were reported by five subjects across the four dose exploration cohorts (diarrhea, n=2; vomiting, anal fissure, anal inflammation, proctalgia, neutropenic infection, neutropenic sepsis, and febrile neutropenia, all n=1), including one subject treated in Part 1A- Cohort B who was included in the pooled analysis (febrile neutropenia)

Treatment-related TEAEs Grade 3 or higher were reported by 41 of 56 subjects, including 22 subjects from the pooled analysis of 32 subjects treated with irinotecan liposome injection 50 mg/m2+LV 400 mg/m2+5-FU 2400 mg/m2 and oxaliplatin 60 mg/m2. The TEAEs included: neutropenia, n=10; febrile neutropenia, hypokalemia, both n=4; diarrhea, nausea, both n=3; anemia, vomiting, both n=2, with no reported Grade 3 or higher fatigue or peripheral neuropathy.

SAEs were reported by 34 of the 56 treated subjects, including 17 of the 32 subjects in the pooled analysis, with 23 subjects reporting treatment-related SAEs. In the pooled analysis, 10 of the 32 subjects had treatment-related SAEs: nausea, febrile neutropenia, both n=3; diarrhea, vomiting, both n=2; colitis, enterocolitis, stomatitis, anemia, pneumonia, and pyrexia, all n=1. At the data cut-off there were no treatment-related TEAEs leading to death.

There were 19 subjects who reported TEAEs leading to discontinuation (including eight subjects in the pooled analysis), with 39 subjects requiring dose adjustment due to AEs (including 26 subjects in the pooled analysis).

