6.2.2 Dose Reduction of Oxaliplatin

- a. If the subject develops persistent grade 2 neurosensory events, the dose of oxaliplatin will be reduced to 48 mg/m^2 for first occurrence, or 36 mg/m^2 for second occurrence.
- b. If the subject develops grade 3 or 4 gastrointestinal toxicities (despite prophylactic treatment) and recovers from them, the dose of oxaliplatin will be reduced to 48 mg/m² for first occurrence, or 36 mg/m² for second occurrence.
- c. If the subject develops grade 4 neutropenia or febrile neutropenia or grade 3/4 thrombocytopenia, the next dose will be delayed until neutrophils 1,500/µL and platelets 75,000//µL. Granulocyte colony-stimulating factor (G-CSF) may be administered as indicated.
- d. If the subject develops persistent grade 3 neurosensory events, discontinue oxaliplatin.

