6.2.3 Dose Reduction of 5-Fluorouracil

- a. 5-fluorouracil will be held for any of the following:
 - Grade 3 or 4 diarrhea
 - Grade 2 or 3 palmar-plantar erythrodysesthesia (hand-foot syndrome)
 - Grade 3 or 4 mucositis
 - Grade 4 myelosuppression
- b. Upon resolution or improvement to Grade 1 diarrhea, mucositis, myelosuppression, or palmar-plantar erythrodysesthesia, resume administration of 5-fluorouracil at 1,920 mg/m² for first occurrence, or 1,440 mg/m² for second occurrence.
- c. 5-fluorouracil will be discontinued following development of any of the following adverse reactions:
 - Angina, myocardial infarction/ischemia, arrhythmia, or heart failure in patients with no history of coronary artery disease or myocardial dysfunction
 - Hyperammonemic encephalopathy
 - Acute cerebellar syndrome, confusion, disorientation, ataxia, or visual disturbance

6.3 **Protocol Therapy Discontinuation**

In addition to discontinuation from therapy related to toxicities as outlined above, a subject will also be discontinued from protocol therapy and followed up per protocol under the circumstances outlined below. The reason for discontinuation of protocol therapy will be documented on the electronic case report form (eCRF).

• Documented disease progression

- The treating physician thinks a change of therapy would be in the best interest of the subject
- The subject requests to discontinue protocol therapy, whether due to unacceptable toxicity or for other reasons
 - If a subject decides to prematurely discontinue protocol therapy ("refuses treatment"), the subject should be asked if he or she may still be contacted for further scheduled study assessments. The outcome of that discussion should be documented in both the medical records and in the eCRF.
- A female subject becomes pregnant
- If protocol therapy is interrupted for ≥ 28 days.

6.4 **Protocol Discontinuation**

If a subject decides to withdraw from the study (and not just from protocol therapy) all efforts should be made to complete the final study assessments. The site study team should contact the subject (ex. telephone, telehealth, clinic visit, etc.) to determine the reason for the study withdrawal. If the reason for withdrawal is an adverse event, it will be recorded on the eCRF.

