11. ADVERSE EVENTS

11.1 Definitions

11.1.1 Adverse Event (AE)

An AE is any untoward medical occurrence whether or not considered related to the study drug that appears to change in intensity during the course of the study. The following are examples of AEs:

- Unintended or unfavorable sign or symptom
- A disease temporally associated with participation in the protocol
- An intercurrent illness or injury that impairs the well-being of the subject

Abnormal laboratory values or diagnostic test results constitute AEs only if they induce clinical signs or symptoms or require treatment or further diagnostic tests. Hospitalization for elective surgery or routine clinical procedures that are not the result of an AE (e.g., surgical insertion of central line) should not be recorded as an AE. Disease progression should not be recorded as an AE, unless it is attributable to the study regimen by the site investigator.

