11.2 Reporting

11.2.1 Adverse Events

- AEs will be recorded from time of signed informed consent until 30 days after discontinuation of study drug(s) and/or until a new anti-cancer treatment starts, whichever occurs first.
- AEs will be recorded regardless of whether or not they are considered related to the study drug(s).
- All AEs will be recorded in the subject's medical record and on the appropriate study specific eCRF form within the EDC system.
- All AEs considered related to study drug(s) will be followed until resolution to ≤ Grade 1 or baseline, deemed clinically insignificant, and/or until a new anti-cancer treatment starts, whichever occurs first.
- Asymptomatic laboratory abnormalities that do not require treatment will not be collected as adverse events.

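### The Grade 3–4 safety endpoint can miss asymptomatic, untreated cytopenias: the adverse-event rules leave them out, and the plan does not say where the grades come from

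*Combined protocol and SAP*

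**What the plan says.** Sections 2.2.2 and 12.2.2 define the safety endpoint as "Safety and tolerability of FOLFOX-nal-IRI; Grade 3 and 4 toxicities as defined by the NCI Common Terminology Criteria for Adverse Events (NCI CTCAE) v5". Section 12.4 adds only that anyone given at least one dose is evaluable and that CTCAE version 5.0 applies. Section 12.6.2 sends the reader back to 12.2.2 for the analysis.

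Two rules govern when a laboratory value becomes an AE:

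- Section 11.1.1: "Abnormal laboratory values or diagnostic test results constitute AEs only if they induce clinical signs or symptoms or require treatment or further diagnostic tests".
- Section 11.2.1: "Asymptomatic laboratory abnormalities that do not require treatment will not be collected as adverse events".

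Neither has an exception for severe grades or for values that change dosing.

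Two dosing rules can be triggered by a blood count alone. Section 6.2.2c says "If the subject develops grade 4 neutropenia or febrile neutropenia or grade 3/4 thrombocytopenia, the next dose will be delayed" until counts recover, with G-CSF optional. Section 6.2.3 lists "Grade 4 myelosuppression" among the reasons to hold 5-fluorouracil (5-FU), which then resumes at a lower dose.

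Blood counts are scheduled on Day 1 of each cycle. Footnote 4 of the study calendar specifies "CBC with differential and platelet count to include WBC, Hgb, ANC and platelet count".

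**The concern.** The endpoint is defined by grade. The collection rule is defined by symptoms and treatment. A severe but silent low count satisfies the first and is excluded by the second.

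This affects the kind of toxicity the protocol expects. Section 1.3.3.1 names lymphopenia and neutropenia as the most common Grade 3 or 4 laboratory abnormalities of the liposomal drug given with 5-FU and leucovorin. For the regimen used here, the related Grade 3 or higher events in Section 1.3.3.1.1 begin with neutropenia: "The TEAEs included: neutropenia, n=10; febrile neutropenia, hypokalemia, both n=4".

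Two things are at stake. First, Section 1.4 hypothesises a tolerable regimen and Section 1.2 criticises FOLFIRINOX for its Grade 3 or 4 toxicity, so a low recorded rate could partly reflect the recording rule. Second, one analyst using AE records and another grading the blood counts could report different rates for the same patients. Sites may also record the same event differently, because the two AE rules conflict.

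**Working it through.** The plan states no figure to reproduce, so the check follows individual events through the rules.

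| Event | AE under 11.1.1? | Collected under 11.2.1? | Written dosing consequence |
|---|---|---|---|
| Febrile neutropenia | Yes, symptomatic | Yes | Next dose delayed (6.2.2c) |
| Grade 4 neutropenia, no symptoms, G-CSF given | Yes, treated | Yes | Next dose delayed; 5-FU held, then reduced |
| Grade 4 neutropenia, no symptoms, managed by waiting and repeat counts | Only if a repeat count is a further diagnostic test | No | Next dose delayed; 5-FU held, then reduced |
| Grade 3/4 thrombocytopenia, no symptoms, untreated | Same ambiguity | No | Next dose delayed; if Grade 4, 5-FU also held, then reduced |
| Grade 3 neutropenia alone, no symptoms, untreated | Same ambiguity if repeated, otherwise no | No | No specific rule; only the any-reason delay in 6.1 |

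**Dose effect.** After a first hold, 5-FU resumes at 1,920 mg/m² instead of 2,400 mg/m². 1,920 / 2,400 = 0.80, a 20% reduction. After a second it is 1,440 / 2,400 = 0.60. An event with this consequence need not appear in the AE data.

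**Conflict between the rules.** Rows three and four show it. An asymptomatic finding that leads to further tests but no treatment is an AE in 11.1.1 and is not collected in 11.2.1.

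**Can the undercount be sized?** Section 1.3.3.1.1 gives 10 related Grade 3 or higher neutropenia events. If the list describes the 32 pooled subjects at these doses, the rate is 10/32 = 31% (exact 95% CI 16% to 50%). If it covers all 56 treated, it is 10/56 = 18% (9% to 30%). Scaled to the target of 28 subjects, that is 28 × 10/32 = 8.75 or 28 × 10/56 = 5.0.

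Let f be the share of such events that is asymptomatic and untreated. If the 10 were a complete count, the number recorded here would be 8.75 × (1 − f) or 5.0 × (1 − f). The documents do not give f. Over its full range of 0 to 1 the result runs from no loss to total loss, which carries no information.

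The starting count is also uncertain. The 10 are reported treatment-emergent AEs from a study whose laboratory collection rule is not described. If that study already left out silent, untreated values, multiplying by (1 − f) would discount twice, and about 8.75 recorded cases would be expected here under a similar rule.

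**Can the endpoint be recovered?** In principle, yes, by grading the scheduled counts. No section says this will be done.

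**The case against.** The strongest reply is that the endpoint speaks of toxicities by CTCAE, not of AE forms, and neutrophil counts are taken every cycle, so grading them would give the haematological rate. That stands: the undercount arises only if AE records are the source. It does not settle the matter, because the plan leaves the source open while giving an explicit rule that keeps these events out of AE records.

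There are also other routes to capture. G-CSF makes an event treated and therefore collected. Waiting for recovery under 6.2.2c needs a repeat count, which a site could treat as a further test under 11.1.1. Section 6 mentions AEs that interrupt treatment, and 11.1.2 cites blood dyscrasias as a possible serious event. These make losing every dose-changing event unlikely. None clearly overrides 11.2.1, since an event must first qualify for collection as an AE.

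Four stronger readings are tempting but unsupported:

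- *All Grade 3–4 neutropenia that changes dosing is lost.* The count-triggered rules name Grade 4 neutropenia, Grade 3/4 thrombocytopenia and Grade 4 myelosuppression. Isolated Grade 3 neutropenia affects dosing only through the any-reason delay in 6.1.
- *The recorded rate will fall by some stated amount.* Neither f nor the earlier study's collection rule is given.
- *Blood counts will not be in the database.* Section 14.2 says that clinical data are generally captured and that selected standard-of-care data are added according to study objectives. Safety is one of those objectives, and the case report forms are not among the documents.
- *The DSMB will have the same blind spot.* Section 13.2 lists an AE summary report, but Section 13.1 also sends data summary reports of unspecified content.

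**Conclusion.** The concern holds in limited form. The written AE rules exclude asymptomatic, untreated laboratory abnormalities at any grade, and they contradict each other on findings that need only further tests. The safety endpoint counts Grade 3 and 4 toxicities without naming its source. If AE records are that source and the rules are followed as written, asymptomatic untreated Grade 3–4 cytopenias can be missed, including some that delay treatment or reduce 5-FU.

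The direction is towards a lower recorded rate; the size cannot be estimated from the documents. Neutropenia is the most frequent related Grade 3 or higher event listed for the prior study (n=10), which shows why the gap matters but not how large it is.

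The endpoint is secondary and descriptive. No test or numeric stopping rule depends on it, and the primary disease control rate analysis is unaffected. The change should be made, but it does not threaten the trial's main conclusion.

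**What to change.** 1. In Sections 11.1.1 and 11.2.1, record as an AE every laboratory abnormality of CTCAE Grade 3 or higher, and any laboratory abnormality that delays, reduces or stops a study drug, regardless of symptoms or treatment. Use the same wording in both.
2. In Section 12.4, state that haematological toxicity is graded from blood-count values, scheduled and unscheduled, and reported as worst grade per treated subject.
3. Note there that cycle-start counts may miss nadirs. Section 10.2.2.5 places 5-FU granulocytopenia at 9 to 14 days, so a count on Day 1 of the next 14-day cycle may come after the lowest value. The graded rate is then still a lower bound.

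The cost is wording, more AE entry, and entry of blood counts if they are not already captured: at most 28 × 12 = 336 cycle-start counts, plus any unscheduled ones. No visits, blood draws or patients are added. The drawback is that the reported Grade 3–4 rate will be higher, and comparisons with studies that used a narrower collection rule will need care.
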